6. IMMUNOGENICITY

6.1. Endpoints

Primary Endpoint:

Magnitude of humoral immune responses against EBOV GP (as measured by binding antibody levels using ELISA [in ELISA units/mL] until the 21-day Post-dose 2 visit).

Exploratory Outcomes:

Several exploratory objectives are specified in the CTP¹. Those objectives will be investigated depending on the availability of the response outcome. The exploratory response outcomes could include but may not be limited to the following:

- Humoral immune responses against EBOV GP as measured by:
 - ELISA (in ELISA units/mL), collected at all timepoints (as specified in the CTP¹).
 - Neutralizing antibody response in titers that inhibit viral infection by a certain percentage (IC₅₀), collected at all timepoints (as specified in the CTP¹).
- Cellular immune responses against EBOV GP as measured by:
 - Number of interferon (IFN- γ) producing T cells (using enzyme-linked immunospot [ELISpot]), at all available timepoints.
 - Percentage of CD4+ T cells producing IFN- γ or interleukin (IL-2) (using intracellular cytokine staining [ICS]), at all available timepoints.
 - Percentage of CD8+ T cells producing IFN- γ or IL-2 (using ICS), at all available timepoints.
- Anti-vector neutralizing antibody responses as measured by Ad26 virus neutralization assay (VNA) (serum titers of neutralizing antibodies to the adenovirus serotype 26 [Ad26] vector 90% inhibitory concentration [IC₉₀]), collected at baseline.

6.2. Immunogenicity Against the Insert

6.2.1. Humoral Immune Responses

6.2.1.1. Parameters

Humoral immune responses, as measured by the following assay, will be analyzed:

- **Binding antibody responses using Filovirus Animal Nonclinical Group (FANG) ELISA:** Quantification of antibodies binding to EBOV GP using the ELISA units/mL readout.

In addition, the following will be defined for ELISA (ELISA units/mL) binding antibody responses:

- **Sample interpretation:** A sample will be considered positive, if the value is above the lower limit of quantification (LLOQ).
- **Responder:**
 - If sample interpretation is negative at baseline but positive post-baseline and the post-baseline value is greater than $2.5 \times \text{LLOQ}$; OR
 - If sample interpretation is positive at both baseline and post-baseline and there is a greater than 2.5-fold increase from baseline (2.5-fold increase on the original scale).
- **Neutralizing antibody responses using virus neutralization assay (VNA):** titers of EBOV GP-specific neutralizing antibodies (unit: 50% inhibitory concentration [IC_{50}]).

For VNA (IC_{50} titer) responses, the following will also be defined:

- **Sample interpretation:** A sample will be considered positive if the value is greater than both the assay-specific LLOQ and $3 \times$ (amphotropic murine leukemia virus [aMLV]) titer. Otherwise, the sample will be considered negative.
- **Responder:**
 - If sample interpretation is negative at baseline but positive post-baseline and the post-baseline value is greater than $2 \times \text{LLOQ}$; OR
 - If sample interpretation is positive at both baseline and post-baseline and there is a greater than 2-fold increase from baseline (2-fold increase on the original scale).

Important: The pseudovirions used in the pseudo VNA (psVNA) are constructed using an HIV-genomic luciferase vector. During assay validation, a high non-EBOV GP-specific background signal was observed for 1 out of 3 HIV-positive sera tested. This could be due to the subjects' antiretroviral therapy interfering with the HIV-genomic luciferase vector-based pseudovirion assay. There is currently an ongoing exploration of assay optimization to improve the sensitivity for the sera from HIV-infected subjects. If assay optimization would not be possible, then an alternative psVNA or a wild-type VNA may be considered for HIV-infected subjects' sera sample analysis. Therefore, the analysis of psVNA described in this SAP will not be applicable to the HIV-infected subjects. The analysis description of the psVNA of HIV-infected subjects will only be made when the optimum (or alternative) assay is found.

6.2.1.2. Data Handling Rules

For ELISA binding antibody responses, values below the LLOQ will be imputed with LLOQ/2. For the calculation of fold increases, the values below LLOQ will be imputed with the LLOQ. For VNA titers, values less than the assay-specific LLOQ or less than $3 \times \text{aMLV}$ will be imputed with half of the assay-specific LLOQ. For the calculation of fold increases, values that are less than the assay-specific LLOQ or less than $3 \times \text{aMLV}$ will be imputed with the assay-specific LLOQ.

Remark: If an aMLV titer (negative control) is a censored value (ie, <40), then it will be imputed with **40** before proceeding with further computations.

6.2.1.3. Analysis Methods

The humoral immune responses (immunogenicity against EBOV GP) will be evaluated separately for each part of the study. Within each part, the data will primarily be presented by vaccination schedule (ie, vaccine sequence and interval) with a distinction between the healthy and HIV-infected cohorts. In addition, the data from Parts 1 and 2 will be pooled (matching cohort and vaccination schedule) and presented by vaccination schedule. Also, the pooled immunogenicity data (ie, ELISA units/mL and VNA (IC_{50})) will be presented by age stratum (aged 18-50 years and aged 51-70 years) for each vaccination schedule. Furthermore, the pooled immunogenicity data (ELISA units/mL and VNA (IC_{50})) will be presented by vaccination schedule without a distinction between the cohorts (ie, healthy and HIV-infected). See Section 2.4 (and Table 4) for details on the subgroup analyses that will be performed.

Except for VNA analysis of the HIV-infected subjects, the humoral immune responses will be analyzed as follows. Summary statistics (ie, geometric mean and corresponding 95% CIs) will be calculated and presented for ELISA binding antibody responses (ELISA units/mL) and VNA titers (IC_{50}) at each time point. The geometric mean fold increase (from Pre-dose and Pre-dose 2) with corresponding 95% CI will also be presented per time point for these parameters.

Graphical representations (on a \log_{10} -scale) of regimen profiles using the geometric mean concentrations with 95% CIs will be presented by vaccination schedule. Regimen profiles of the geometric mean concentrations with 95% CIs will also be generated by vaccination schedule and pre-existing antibody response against Ad26 vector (ie, pre-existing Ad26 versus not pre-existing Ad26). In addition, graphs of the reverse cumulative distributions (ie, percentage of subjects versus the magnitude of the antibody response levels) will be provided for the following time points, if available:

- Baseline and Pre-dose 2
- Baseline and 21 days Post-dose 2
- Baseline and 42 days Post-dose 2
- Baseline and 180 days Post-dose 2
- Baseline and 365 days Post-dose 2

For both ELISA (ELISA units/mL) and VNA (IC_{50} titer), additional graphical representations (on a \log_{10} -scale) will be provided using dot plots (with distinction between positive and negative sample interpretations), by vaccination schedule.

Responder rates and positive sample interpretation will be summarized (ie, showing number, percentage and the exact 95% Clopper-Pearson CI) for ELISA (ELISA units/mL) antibody responses and VNA (IC_{50}) titers per time point.

Furthermore, response patterns over time for the humoral immune responses will be analyzed, taking into account the within-subject correlations, to describe differences between the vaccination schedules at the 21-day Post-dose 2, 42-day Post-dose 2, 6-month Post-dose 2 and 1-year Post-dose 2 visits. A linear mixed model with the unstructured variance-covariance and an unstructured mean (ie, including time as a categorical variable) will be used to estimate the geometric mean concentrations and the associated 95% CI at these timepoints. In case of model convergence problems, another variance-covariance structure (eg, heterogeneous compound symmetry, compound symmetry or simple) will be used.

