analysis of adverse events did not show any consistent pattern suggestive of an association of Ad35.CS.01 or Ad26.CS.01 with specific adverse events. There were no serious adverse events reported during the study. No subject discontinued during a study phase (vaccination or challenge) due to adverse events. One subject in the high-dose group completed the vaccination phase and the final safety follow-up visit but did not take part in any challenge phase activities because of ongoing dyspnea. The most common related adverse events after each vaccination were injection site pain, malaise, headache, myalgia and chills. The incidence of vaccine-related adverse events was generally higher in the high-dose group than in the low-dose group. In general, incidence of malaise, headache, and myalgia were higher after the third dose (Ad26) than after the first or second doses (Ad35). Injection site pain was more commonly reported in the low and high-dose groups than by placebo subjects. There were no clinically significant changes in laboratory test parameters or vital signs data.⁵

Based on the previous clinical experience of Ad26 vector with different inserts, there has been no impact of Ad26 seropositivity on subjects' safety and only limited impact on immunogenicity results. Therefore, there are no safety concerns with regard to the inclusion of Ad26 seropositive subjects in the study, and the study subjects will not be screened for Ad26 seropositivity as part of the study eligibility criteria. The purpose of the Ad26 seropositivity assessment at baseline is to evaluate its impact, if any, on vaccine immunogenicity.

Safety Profile of MVA-BN

MVA-BN is a further attenuated version of the MVA virus, which in itself is a highly attenuated strain of the poxvirus Chorioallantois Vaccinia Virus Ankara. MVA-BN induces strong cellular activity as well as a humoral (antibody) immune response and has demonstrated an ability to stimulate a response even in individuals with pre-existing immunity against Vaccinia. One of the advantages of MVA-BN is the virus' inability to replicate in a vaccinated individual. The replication cycle is blocked at a very late stage, which ensures that new viruses are not generated and released. This means that the virus cannot spread in the vaccinated person and none of the serious side effects normally associated with replicating Vaccinia viruses have been seen with MVA-BN.

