6.2.2.3. Analysis Methods

The cellular immune responses will be evaluated separately for each part of the study. Within each part, the data will primarily be presented by vaccination schedule with a distinction between the healthy and HIV-infected cohorts. The cellular data will not be presented by age stratum. Also, the cellular data for healthy and HIV-infected cohorts will not be combined for analysis. See [Table 4](#) for details.

Summary statistics (ie, median, quartiles [Q1, Q3]) will be presented for all continuous cellular immunogenicity outcomes (ie, ELISpot and ICS) at each time point. Also, the median fold increases (from Pre-dose 1 and Pre-dose 2) with the corresponding quartiles (Q1 and Q3) will be presented for ELISpot only.

Graphical representations (on a \log_{10} -scale) will be provided using dot plots, by vaccination schedule. Also, regimen profiles of the vaccination schedules showing the median and the quartiles (Q1 and Q3) will be presented. Other profiles (median and quartiles) will be generated by pre-existing antibody response against Ad26 vector (ie, pre-existing Ad26 versus not pre-existing Ad26 vector). Responder and positive sample interpretation rates will be summarized

(ie, showing number, percentage and the corresponding exact 95% Clopper-Pearson CIs) per timepoint.

For ICS, the proportions of EBOV GP-specific CD4+ and CD8+ T cells (ie, cells producing at least 1 of the 3 investigated cytokines) will also be tabulated per timepoint and shown in a pie chart. The magnitude of each cytokine subset will be shown in a bar chart. Both pie chart and bar chart will be restricted to responders.

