6.3. Immunogenicity Against the Vector

6.3.1. Humoral Immune Responses

6.3.1.1. Parameter

Immune responses, as measured by the Ad26 VNA (serum titers of neutralizing antibodies to the Ad26 vector [IC₉₀]) will be analyzed. The following will also be defined for Ad26 VNA titers:

Sample interpretation: a sample will be considered positive, if the value is above the assay-specific LLOQ.

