6.3.1.2. Data Handling Rules

For the outcome (ie, Ad26 VNA), values below the LLOQ will be imputed with half of the LLOQ (LLOQ/2).

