6.3.1.3. Analysis Methods

The humoral immune responses (ie, immunogenicity against Ad26 vector) will be evaluated separately for each part of the study. Within each part, the data will primarily be presented by cohort (ie, healthy and HIV-infected) and vaccination schedule.

The geometric mean and corresponding 95% CIs will be calculated. Positive sample interpretation will be summarized (ie, showing number, percentage and the exact 95% Clopper-Pearson CI). A data listing will also be generated.

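### Baseline Ad26 titre is related to the vaccine response only through a pre-existing/not split, so the plan gives no measure of association and no view of gradation among positives; how much is lost depends on a seropositive share the documents do not give.

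*SAP*

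**What the plan says.** Protocol 1.1 explains why subjects are not screened for Ad26 antibodies and then states: "The purpose of the Ad26 seropositivity assessment at baseline is to evaluate its impact, if any, on vaccine immunogenicity". SAP 6.1 lists, as an exploratory outcome taken at baseline, "Anti-vector neutralizing antibody responses as measured by Ad26 virus neutralization assay (VNA") and specifies the readout as "serum titers of neutralizing antibodies to the adenovirus serotype 26 [Ad26] vector 90% inhibitory concentration". SAP Table 4 lists this assay for Part 2 only.

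Two rules turn the titre into analysis data. SAP 6.3.1.1: "a sample will be considered positive, if the value is above the assay-specific LLOQ". SAP 6.3.1.2: "values below the LLOQ will be imputed with half of the LLOQ (LLOQ/2"). The titre is then summarised on its own in SAP 6.3.1.3: "The geometric mean and corresponding 95% CIs will be calculated", with a positivity rate and a listing.

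Two outputs link Ad26 to the vaccine response. For ELISA and VNA, SAP 6.2.1.3 plans geometric mean profiles with 95% CIs "by vaccination schedule and pre-existing antibody response against Ad26 vector (ie, pre-existing Ad26 versus not pre-existing Ad26"). For cellular responses, SAP 6.2.2.3 says: "Other profiles (median and quartiles) will be generated by pre-existing antibody response against Ad26 vector". The mixed model in 6.2.1.3 names no Ad26 term. No scatter plot, correlation, regression or set of titre categories against response is planned.

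**The concern.** The assay returns a titre, but wherever the titre meets the response it has become a yes/no label. A subject just above the cut and one with a very high titre are plotted as the same. If vector immunity reduces the response, a natural expectation is that the reduction grows with titre, and two group curves cannot show that. If most subjects are positive, the comparison also rests on a small negative group.

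A more basic gap sits beside this one: the profiles carry no estimate of the difference or association at all. At stake is whether the trial can say anything quantitative on the question given as the reason for the assay. The primary safety and immunogenicity analyses are unaffected.

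**Working it through.** **Inputs from the documents.** Active subjects per cohort in Part 2: 160 (28-day schedule) and 40 (14-day schedule). ELISA SD up to 0.5 log10, two-sided 5%, 90% power (protocol 11.1, Table 5, stated for Day 42 post-boost).

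**Assumptions, not in the documents.** Share above the LLOQ: 10 to 95%. Log10 titre normal with SD 0.5 to 0.8. Effect on log response linear in log titre, unless stated otherwise. Pre-existing is taken to mean above the LLOQ. Power serves only as a measure of information, since no test is planned.

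**1. Reproducing the plan's nearest figure.** The plan states no figure for the Ad26 question. Table 5, 160 versus 160, SD 0.5: (1.960 + 1.282) × 0.5 × √(1/160 + 1/160) = 0.181, or 0.182 with the noncentral t. Stated: 0.18. It reproduces.

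**2. What a yes/no comparison could detect.** Same noncentral-t method, SD 0.5, 90% power:

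| Cohort | 50/50 | 80/20 | 90/10 |
|---|---|---|---|
| n=160 | 0.26 log10 | 0.32 | 0.43 |
| n=40 | 0.53 | 0.66 | 0.88 |

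The 90/10 entry for n=160 compares 144 with 16 subjects; 10^0.43 is about 2.7-fold.

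**3. Information kept by the split, linear effect.** For a normal log titre cut at c with share p above, the squared correlation of the indicator with the titre is φ(c)²/[p(1−p)]. At p = 0.8: 0.280²/0.16 = 0.490. The fair comparator is the titre as the SAP codes it, with LLOQ/2 below the limit; this was simulated with 1,000,000 draws. The last column is split divided by coded titre.

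| Share positive | Split | Coded titre (SD 0.5 / 0.8) | Kept by split |
|---|---|---|---|
| 10% | 0.342 | 0.349 / 0.336 | 98–102% |
| 20% | 0.490 | 0.523 / 0.507 | 93–96% |
| 30% | 0.576 | 0.646 / 0.630 | 89–91% |
| 50% | 0.637 | 0.815 / 0.802 | 78–79% |
| 70% | 0.576 | 0.920 / 0.914 | 63% |
| 80% | 0.490 | 0.956 / 0.953 | 51% |
| 90% | 0.342 | 0.982 / 0.982 | 35% |
| 95% | 0.224 | 0.992 / 0.993 | 22–23% |

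**4. The same on a power scale.** Power = Φ(atanh(r)·√(n−3) − 1.96). Take the correlation that a fully observed titre would detect with 90% power at n=160: tanh(3.242/√157) = 0.253. Coded titre (SD 0.6) versus split: 64% vs 61% at 20% positive, 83% vs 73% at 50%, 89% vs 61% at 80%, 90% vs 46% at 90%.

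A separate simulation (correlation −0.25, n=160, Spearman on tied titres versus a t-test on the split) agrees: 44% vs 45% at 10%, 62% vs 62% at 20%, 71% vs 69% at 30%, 80% vs 72% at 50%, 87% vs 60% at 80%, 87% vs 46% at 90%. With n=40 and 80% positive it gives 32% vs 20%.

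**5. Step effect at the LLOQ.** The ranking reverses. The split loses nothing, and the coded titre (SD 0.6) keeps 84% of the information at 10% positive, 80% at 20%, 70% at 50%, 50% at 80% and 35% at 90%. With a step sized so that the split has about 79% power at n=160, Spearman has 76% at 30% positive, 70% at 50%, 46% at 80% and 27% at 90%.

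**The case against.** The protocol words the assessment as one of seropositivity, which is a status, and a two-group display addresses status directly. The purpose stands in Background; it is not a listed objective or endpoint. The study is descriptive, so power comparisons describe tests nobody plans. Nothing collected is discarded: titres are listed, and SAP 6.1 leaves the exploratory outcomes open-ended, so the extra plot could be added at any time. Cellular responses are themselves only optional (SAP 6.2.2.1).

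Much of this stands. It makes the point an improvement to an exploratory display and makes any ELISpot version conditional. It does not supply what the plan lacks: a measure of association, or a view of response across titres among positives. A scatter plot with a correlation and CI is as descriptive as the profiles.

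Three stronger readings are tempting and are not supported:

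- A reader might infer that the split certainly wastes much of the information. The documents give no seroprevalence, titre distribution or LLOQ value, and the loss runs from nothing upwards.
- A reader might infer that the titre analysis should replace the split. Step 5 shows that this would be worse if the effect is a step.
- A reader might infer that an apparent null here would support not screening on Ad26 status. Protocol 1.1 rests that choice on earlier experience with Ad26 vectors, and nothing ties these profiles to a screening decision.

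**Conclusion.** The point holds as a low-cost improvement. The baseline titre is quantitative, its purpose is stated, and every planned link to the response is a yes/no profile without an estimate of association. For an effect linear in log titre, the split loses 0 to about 11% of the information at 10 to 30% positive, about a fifth at 50%, half at 80% and two thirds at 90%. For a step at the LLOQ it loses none. These sizes rest on the assumed normal log titre, on the unknown share positive, and on reading pre-existing as above the LLOQ. That reading is an inference from the positivity rule in SAP 6.3.1.1, because neither 6.2.1.3 nor 6.2.2.3 defines the term.

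**What to change.** In SAP 6.2.1.3:

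1. State that pre-existing means a baseline Ad26 VNA titre above the assay LLOQ (6.3.1.1), if that is what is intended.
2. For active Part 2 subjects, by schedule and cohort, add a scatter plot of log10 ELISA at 21 days Post-dose 2 against log10 baseline Ad26 VNA titre. Report the Spearman correlation and its 95% CI, with values below the LLOQ set to LLOQ/2 as in 6.3.1.2. Being rank-based, the coefficient treats these values as ties and does not depend on the imputed value.
3. Do the same for ELISpot if that assay is analysed.
4. Keep the existing profiles, report both together, and base any statement on Ad26 impact on both.

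Cost: one paragraph and one figure/table shell, using data already collected. The downside is a few more exploratory outputs, to be labelled as unadjusted. In the 40-subject cohorts the interval will be wide: roughly ±1.96/√37 = ±0.32 on the Fisher z scale.

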6.2.2. Cellular Immune Responses

6.2.2.1. Parameters

Cellular immune responses, as measured by the following assays, may be analyzed:

- **Enzyme-linked immunospot (ELISpot):** EBOV GP-specific $IFN-\gamma$ producing T cells, measured as the number of spot-forming units per million peripheral blood mononuclear cells (SFU/ 10^6 PBMC).

The following will be defined for ELISpot:

- **Sample interpretation:** Sample positivity criteria will be defined by vendor based on the assay characteristics. A false positivity criterion of less than 10% for naïve samples (from non-vaccinated subjects) will be applied.
- **Responder:**
 - If sample interpretation is negative at baseline but positive post-baseline and the post-baseline value is greater than $2\times$ positivity threshold; OR
 - If sample interpretation is positive at both baseline and post-baseline and there is a greater than 2-fold increase from baseline.
- **Intracellular cytokine staining (ICS):** The following responses will be measured:
 - CD4+: IL-2+ and $IFN-\gamma$ + responses to EBOV GP.
 - CD8+: IL-2+ and $IFN-\gamma$ + responses to EBOV GP.

In addition, using $IFN-\gamma$ + and IL-2+ as present in the database for each T cell type, the following will be defined for the ICS:

- **Sample interpretation:** The sample positivity (interpretation) will be determined for each of the two peptide pools separately. If a sample is considered positive for at least one of the peptide pools the sample is considered positive. If a sample is positive for either IFN- γ + or IL-2+, it is considered positive. A sample is considered positive when the EBOV peptide pool stimulated readout is greater than 3-fold the mock (unstimulated) readout and the mock-subtracted value is greater than the threshold (limit of detection (LOD)).
- **Responder:** The responder status of a subject will be determined based on IFN- γ + and IL-2+ separately. This will be done on the mock subtracted percentages for the combined peptide pools (ie, sum of GP1 and GP2). For a given time point, if a responder status is achieved based on either IFN- γ + or IL-2+, then the subject will be declared as a responder at that time point. For a given time point, a subject is considered as a responder when either of the following condition is satisfied:
 - If sample interpretation is negative at baseline but positive post-baseline and the post-baseline value is greater than $2\times$ LOD; OR
 - If sample interpretation is positive at both baseline and post-baseline and there is a greater than 2-fold increase from baseline in background adjusted percentage of the combined peptide pools.

For additional rules for the ICS analysis refer to Attachment [52.5](#).

